3.0 GENERAL CONSIDERATIONS

3.1 Terminations

There are multiple types of terminations in this study, end of study medication, medical management termination and study termination. Study medication will be discontinued in the event of intolerable side effects, safety concerns preventing further medication treatment (i.e., pregnancy), relapse, or the end of the 24-week active treatment phase. Participants discontinuing medication, but not yet meeting relapse criteria, prior to week 24 will continue within the same study assessment schedule. Participants meeting relapse criteria will discontinue medication, research visits and complete a medical management termination form. All participants who end treatment early (prior to week 21) will be encouraged to attend a visit at week 24 and will be seen in long-term follow-up (weeks 28 and 36). In all cases of treatment discontinuation, the research team will make an effort to arrange for continued community treatment, as appropriate and available, including further XR-NTX and BUP-NX, or methadone maintenance and intensive outpatient psychosocial aftercare. For participants receiving BUP-NX, who do not wish to continue, or for whom community resources are not available, the study will provide a two-week BUP-NX taper, if clinically appropriate.

Dropout from treatment is a typical failure mode for the treatment of opioid dependence with both XR-NTX and BUP-NX. A sensitivity analysis will be performed to examine the impact on the hazard ratio and its confidence limits of alternative endpoint definitions. In particular for the primary endpoint, individuals who withdraw will be considered events if they fail to provide weekly urine specimens. An alternative to the protocol definition which introduces these as censored observations will be examined. The analyses of these events can be complex as standard assumptions (missing at random) may not be plausible.

Other outcome variables (opioid and other substance use over time, craving, mood, etc.) will have missing data due to missed visits and dropout from treatment and from study participation. The generalized linear model, or mixed effects model frameworks that will be used for analyses, works with what data are gathered, and assumes missing data are missing at random. For selected secondary outcome analyses, sensitivity analyses will be considered to examine the stability of estimated treatment effects in the face of departures from the assumption of missing at random.

Aggressive tracking procedures will be put into effect to attempt to locate participants and re-engage them, and to minimize missing data. These procedures will be detailed in the study MOP. The greatest likelihood of violation of the assumption of missing at random derives from dropouts, since participants assigned to XR-NTX may dropout from the study for different reasons than participants assigned to BUP-NX, creating the potential for differential attrition. Differential study attrition for the two treatment groups, where outcome differs between the dropouts is a threat to the validity of the outcome analysis. Minimizing the rate of study dropout and loss to follow-up, through aggressive tracking and follow-up, serves to reduce this threat. At a minimum the data gathered on dropouts can be used to test the assumption of missing at random, by examining whether dropouts from the different treatment assignments have similar or different outcomes.

3.2 Study Modification for Differential Treatment Initiation

To maximize generalizability, this study has been designed to permit entry of participants throughout the opiate detoxification process and early abstinence. At the time the study was designed, it was understood that community-based practice of detoxification and medication induction would vary across sites and across patients within sites. It was further decided that the

protocol would allow this variation in community based practice of detoxification-induction, consistent with the aims of an effectiveness trial to test the medications under real world conditions. It was also anticipated that induction onto BUP-NX would be easier than induction onto XR-NTX for patients who are randomized “early” while opioids are still in their system. This is because BUP-NX can be safely initiated while opioids are still in the system, as long as some signs of withdrawal begin to develop, while for XR-NTX one needs to wait until detoxification is completed. This delay is an opportunity for differential attrition between the 2 study arms. The concern is that a higher induction failure rate on XR-NTX, among those randomized early, will contribute to differences in outcome (time-to-relapse) across the 6 month trial, with induction failure leading to relapse. If this is the case, then the interaction between early vs. late randomization and treatment assignment on the primary outcome (time to relapse) becomes germane.

Therefore, after the entry of 100 “early randomizers” (as defined in Protocol Section 8.3 [or Section 1.5 above]) we will compare the induction success rate in these early randomizers on XR-NTX vs. BUP-NX with a test of difference between proportions. The decision rule has >80% power ($\alpha=2.5\%$ 1 tail) to identify differences of .25 or greater if the true initiation rate for the BUP-NX is in the expected range ($\geq .85$). If the difference in induction failure rate is statistically significant, then the following plan will be followed:

1. Increase the sample size to end enrollment at such time as 350 late randomizers have been enrolled to increase power to estimate the difference in primary outcome (time-to-relapse) in this late randomizer group. It is projected that at such time the total N will be approximately 600.
2. Amend the data analysis plan to incorporate an interaction term in the analysis model.

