5.2.2 Induction Status Analysis

The null hypothesis is:

$$H_0 : p_{XR-NTX} = p_{BUP-NX}$$

$$H_A : p_{XR-NTX} \neq p_{BUP-NX}$$

Where p_{XR-NTX} is the proportion of early randomizer participants in the XR-NTX group who were inducted and p_{BUP-NX} is the proportion of early randomizers participants in the BUP-NX group who were inducted. The Fisher's exact test will be used to determine statistical significance at a significance level of 0.05.

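### The early-randomizer decision rule is credited with more than 80% power, but the Fisher exact test that the SAP names for it has about 76% to 78% at .85 versus .60

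*SAP*

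**What the plan says.** SAP 3.2 and Protocol 12.3 plan to compare induction success between the arms once 100 early randomizers have entered, "with a test of difference between proportions". At a one-tailed 2.5% level, both then state: "The decision rule has >80% power" "to identify differences of .25 or greater", provided that the true BUP-NX initiation rate is at least .85. Neither section names the test more closely.

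SAP 5.2.2 does name it, against a two-sided alternative: "The Fisher's exact test will be used to determine statistical significance at a significance level of 0.05". SAP 5.2 limits the analysis to the first 100 early randomizers. SAP 1.5 sets 1:1 allocation, stratified by site and level of opioid use but not by timing of randomization.

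**The concern.** Fisher's exact test is conservative at this sample size, so a power figure worked out for a large-sample test of proportions does not carry over to it. The sentence promises more than 80% over a whole region: every difference from .25 upward and every BUP-NX rate from .85 upward. The boundary point, .85 versus .60, belongs to that region and is its least favourable corner.

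The rule is the trial's one adaptive decision. It governs whether enrolment grows from 400 to about 600 and whether timing of randomization and its interaction with treatment enter the primary model. A reader who judges how well that decision was protected needs the power of the test actually specified.

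**Working it through.** **Inputs.** 100 early randomizers (SAP 5.2); 1:1 allocation (SAP 1.5), taken as 50 per arm; BUP-NX rate .85 and difference .25 (SAP 3.2), hence XR-NTX .85 − .25 = .60; one-sided 2.5% (SAP 3.2) or two-sided 5% (SAP 5.2.2).

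**Step 1: reproduce the stated figure with an uncorrected test.** Pooled-variance normal approximation:

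- Mean rate: (.85 + .60)/2 = .725
- SE under the null: √(2 × .725 × .275/50) = .0893
- SE under the alternative: √((.85 × .15 + .60 × .40)/50) = .0857
- Power: Φ((.25 − 1.96 × .0893)/.0857) = Φ(.874) = 80.9%

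Exact enumeration of the uncorrected z test gives 81.9%. The claim of more than 80% is therefore reproduced for this kind of test.

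**Step 2: use the test that SAP 5.2.2 names.** Power is the sum, over all outcomes (i, j), of P(i; 50, .85) × P(j; 50, .60), both binomial, counting the outcomes where Fisher's p is .05 or less. The result is **75.8%**. One-sided Fisher at .025 gives the same 75.8%, so the difference in sidedness between SAP 3.2 and 5.2.2 does not explain the gap.

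**Step 3: vary the split,** which the design does not fix (.85 versus .60):

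| BUP-NX / XR-NTX | Fisher, two-sided .05 | Fisher, one-sided .025 |
|---|---|---|
| 50/50 | 75.8% | 75.8% |
| 52/48 | 78.5% | 76.1% |
| 48/52 | 77.3% | 76.0% |
| 45/55 | 78.1% | 74.0% |
| 55/45 | 78.1% | 78.0% |

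All are below 80%.

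**Step 4: find where the stated figure does hold,** with 50 per arm:

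| BUP-NX vs XR-NTX | Fisher power |
|---|---|
| .88 vs .63 | 79.3% |
| .89 vs .64 | 80.6% |
| .90 vs .65 | 82.0% |
| .85 vs .59 (difference .26) | 78.9% |
| .85 vs .58 (difference .27) | 81.8% |

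At .85 versus .60, about 56 per arm would be needed (80.8%).

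**The case against.** Four arguments can be made for the plan.

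- **The figure is not a miscalculation.** A reader might infer an arithmetic error. The documents do not support that: the power sentence speaks only of a test of proportions, and for an uncorrected one it is right. Protocol 12.3 never mentions Fisher's test, so its figure is consistent with its own loose description. This stands. The fault is a mismatch between the power sentence and the test named later in the SAP.
- **The risk of missing a difference has passed.** A reader might infer that the trial still runs about a 24% chance (100 − 75.8) of failing to trigger the modification, or that its sample size or primary model is compromised. Neither follows. Protocol 6.2 and 8.3 describe the assessment in the past tense, and SAP 5.3.3 says that the interim result pointed to differential initiation and that the modification will be used. Low power bears only on failing to trigger. This also stands.
- **The 75.8% depends on an exact 50/50 split.** It does, and 50/50 is the least favourable of the splits tried under the two-sided test. The other four fall 1.5 to 2.7 points short of 80%. The gap narrows but does not close.
- **Only the edge of the region fails.** With 50 per arm, Fisher's test has 89.9% power at .95 versus .70 and 88.7% at .85 versus .55. That is correct, but the sentence makes its claim for the edge too.

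A mid-p version of Fisher's test would reach 80.5% at 50/50 (one-sided .025). SAP 5.2.2 does not specify it, although SAP 7.4.1 does name a mid-p version for adverse events.

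**Conclusion.** The point holds as an inconsistency in a stated design property. With the test in SAP 5.2.2, power at .85 versus .60 is about 76% at 50/50 and about 76% to 78% (two-sided .05) across the splits tried, against a stated figure above 80%. The shortfall is roughly 2 to 4 percentage points below 80%, confined to the lower edge of the stated range.

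This rests on three assumptions: the .60 derived from .85 − .25, independent binomial outcomes, and splits between 45/55 and 55/45. The thresholds of .89 and .27 apply to 50 per arm only; at the four unequal splits, two-sided power already passes 80% at a BUP-NX rate of .87. The correction changes the described operating characteristic of the adaptive rule. It does not touch the final analysis, the sample size or any error rate.

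**What to change.** Keep Fisher's exact test. In SAP 3.2, replace the power sentence with: *With Fisher's exact test on 100 early randomizers, power is about 76% to 78% for initiation rates of .85 versus .60, depending on the split between arms; with 50 per arm it is at least 80% if BUP-NX initiation is about .89 or higher (difference .25), or if the difference is at least about .27 (BUP-NX .85).*

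In Protocol 12.3, add that the figure above 80% assumes an uncorrected large-sample test of two proportions.

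Do not switch to a chi-square test to rescue the figure. The assessment has been run, and renaming a decision test once its result is known would be worse than the mismatch. The cost is one sentence per document and a slightly less favourable stated power; no new analysis is needed.

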3.3 Sample Size and Power Calculations

The therapeutic strategies defined above will be evaluated and compared in a two-arm randomized open-label multi-center trial.

Original Projected Sample Size: 200 per treatment group. N = 400 total.

Data Analysis Modification Projected Total Sample Size: N~600 total sufficient to enroll 350 late randomizers.

[figure not shown]
Rationale: The primary outcome is the time to relapse as defined above. Meta-analyses of randomized controlled trials of BUP-NX maintenance treatment for opioid dependence suggest that approximately 50% of patients are retained in BUP-NX treatment with good clinical outcome over 6 months. (Mattick and Kimber 2008). Extended release naltrexone preparations have had few prior randomized comparisons but observations from a recent Russia-based trial evaluating the XR-NTX dose and formulation proposed for this trial had good results with 53% receiving all monthly injections and retained for 6 months. Direct randomized comparison of these approaches has not been performed.

We evaluate the anticipated variability of the primary terminal results by simulating under exponential distributional assumptions with event (relapse) grouping after the first 21 days and using proportional hazards without censoring. Let one treatment have a 6-month success rate of 40% with exponential failure. We use a lower success target than indicated in the above paragraph because the use of the early randomization time point is expected to increase the percentage of participants who are failures. There would be minimal impact on detectable alternatives if a higher 50% success rate was used. From the plot below, we observe that the 95% CI width for the hazard ratio for the 50th percentile of the simulation results under both the null and alternative hypotheses decreases by 31%, 19%, and 14% as the sample size increase

by 50/arm from a base of 50/arm. CI width decreases by 11% when the sample size increases from 200/arm to 250/arm. We have selected 200/arm as subsequent precision improvements with these criteria are close to 10% per 100 sampling units.

Beyond a sample size of 150 to 200 patients per group, further increments in sample size (200 per group, 250 per group, 300 per group, etc.) yield diminishing returns in terms of only relatively small further narrowing of the 95% confidence interval. The rationale for increasing the total sample size to N ~600, in the event of a significant difference in induction success rate among early randomizers, is that given the current ratio of early to late randomizers, N ~600 total will yield approximately 250 early randomizers and 350 later randomizers. 350 late randomizers (N = 175 per treatment group) is close to the 400 (N = 200 per group) originally planned, and will yield a very similar (only slightly wider) 95% confidence interval. This will preserve the intent to achieve a relatively precise estimate of the difference in relapse rates among late randomizers.

Figure 1: Simulation results for the 50th and Upper 95th percentile of the 95% Confidence Interval Widths for the Hazard Ratio, selected sample sizes with lambda=0 and lambda=0.678

The decision theoretic properties of n=200/arm is evaluated further under a decision theoretic approach and using the logrank test. With two-sided alpha = 0.05, N = 400 total participants provides 90% power to detect a hazard ratio of .63 for the second treatment. Table 2 provides additional characterization of power characteristics of the sample size.

Table 2: Detectable Alternatives and Power for 2-tailed 5% level logrank test without censoring Null distribution has a 40% 6 month success rate, N1=N2=200		
Power (%)	Hazard Ratio	6 Month Survival Rate (%) under the Alternative
90.0	.633	56.0
80.0	.678	53.8

Note that inclusion of the baseline level of opioid dependence severity stratification variable in the statistical model as a covariate may increase power and narrow the confidence limits on treatment hazard ratios, should divergent success rates be present in the strata groupings.

Secondary analyses of moderators of treatment effect are important to trial sample size selection. With approximately 200 XR-NTX cases evenly split between two levels of a classifying variable, we would have 79% power to detect, using a two-tailed 5% level test of a binary endpoint, a 20 percentage point difference between the groups. Thus the selected sample size would be relatively robust in its ability to determine whether there are important differences in therapeutic success rates for major demographic or baseline clinical factors.

3.4 Interim Analysis

The study will undergo safety monitoring by the designated DSMB. Both therapies are standard therapies with regulatory approval for treatment of opiate abuse. The treatment strategies have not been directly compared before and classic interim efficacy monitoring is not planned as both are considered acceptable therapies. An adaptive strategy for addressing substantial differential treatment initiation is described above and in Section 5.2.

3.5 Software

All analyses will be performed utilizing SAS® version 9.3. All statistical tests will be conducted at the 5% Type I error rate (two-sided). When multiple tests are conducted, the chance of finding a significant difference in one of the tests, when in fact no difference exists, is greater than the stated Type I error rate. The investigators are aware of the multiple testing issues and will interpret results with caution and use confidence intervals where possible.

3.6 Analysis Populations

Each primary and secondary efficacy outcome measure will be analyzed for the intent-to-treat (ITT) and evaluable population. The intent-to-treat principle is that participants will be analyzed in the groups to which they were randomized, regardless of whether they received the randomized study medication. Another analysis population of interest is the as-treated population. The as-treated population will consist of only participants who were inducted onto study medication.

Major differences in the results for the ITT and as-treated populations, if any, will be further explored. While there is every intention to be complete in describing the analyses to be performed, it is not possible to anticipate every contingency, and some adjustments may be required to meet constraints posed by the structure of the data. Constraints such as non-linearity, non-normality, etc. may lead to different but more appropriate approaches to analysis.

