10.0 PARTICIPANT DISCONTINUATION, FOLLOW-UP

10.1 Treatment Discontinuation

Study medication is discontinued in the event of intolerable side effects, safety concerns preventing further medication treatment (i.e., pregnancy), relapse, or the end of the 24-week active treatment phase (see MOP). Participants discontinuing medication, but not yet meeting relapse criteria, prior to week 24 continue within the same study assessment schedule. Participants meeting relapse criteria discontinue medication and research visits. All participants who end treatment early (prior to week 21) are encouraged to attend a visit at week 24 and are seen in long-term follow-up (weeks 28 and 36). In all cases of treatment discontinuation, the research team makes an effort to arrange for continued community treatment, as appropriate and available, including further XR-NTX and BUP-NX, or methadone maintenance and intensive outpatient psychosocial aftercare. For participants receiving BUP-NX, who do not wish to continue, or for whom community resources are not available, the study will provide a two-week BUP-NX taper, if clinically appropriate.

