Phase 1: Informed Consent, Screening, and Randomization (Days -15 through Day 0): This phase begins with informed consent during the index admission, and initiates enrollment, the conduct of all study-specific procedures and the collection of study data. During the first several days of an index admission, clinical and/or research staff will provide information about the study to potential participants (for scheduled admissions this information may be provided in advance of the admission). Guidelines for opioid detoxification are provided in the study MOP; data on detoxification utilization will be collected. This phase may take place from 1 day to 15 days. Following final review and confirmation of all eligibility criteria, randomization may proceed. Randomization may take place on the same day as informed consent and screening if recent liver function results are available, but in most cases will likely take place 2 or 3 days

later. Regardless of when randomization takes place, the date of randomization will be defined as “Day 0”.

Phase 2: Induction (Day 0 through Day 156): Following randomization, participants will be inducted onto their assigned active medication condition and treated as outpatients for 24 weeks per protocol. Guidelines for induction onto XR-NTX and onto BUP-NX are provided in the study MOP. Following induction, XR-NTX will be administered by injection approximately every 4 weeks; and BUP-NX will be quickly titrated upwards to maintenance doses. Induction should occur as soon as practicable following randomization, but may occur as late as week 22. Participants will continue into Phases 3 and 4 for research visits, even if not yet inducted onto their assigned medication.

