5.2.1 Induction Status Determination

A participant's induction status will be a binary variable of Yes or No. For the participants randomized to BUP-NX, participants will be defined as inducted onto the study medication if he/she has been dispensed medication as measured on the BUP-NX dose log; otherwise, the participant will be defined as not being inducted onto study medication. In a similar manner, for participants randomized to XR-NTX, participants will be defined as inducted onto the study medication if he/she has received an injection of the study medication. Note, the definition of induction status is not dependent upon the number of days for induction to occur.

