5.3.1 Primary Outcome Criteria

Relapse assessment starts Day 21 post-randomization with the day of randomization as Day 0 and ends at the Week 24 visit. As noted above, relapse is defined in two ways:

- a) Four consecutive opioid use weeks
 - i) There are three ways that a use week can be established:
 - (1) Participant self-reports at least one day of use during that week

The self-report of use is measured between the weekly visits and thus does not always include the review of exactly seven days. At the weekly visit, if the previous visit was missed, the participant's daily self-report opioid use is assessed from the start of the current visit window (i.e. the beginning of the window as specified by the protocol calendar, see table below) to the day before the current visit. Conversely, if the previous visit was attended, the participants daily self-report opioid use is assessed from the previous visit attended day to the day before that current visit. Note, only participants self-report collected on or after Day 21 is used in evaluating whether the week is a use week. Thus, if the Week 3 visit is attended on Day 21, there cannot be a use week based on self-reported opioid use.

Visit Number	Target Day	Beginning Window (Days)	End of Window (Days)
00R	00	00	00
01	06	3	12
02	13	10	16
03	20	17	23
04	27	24	30
05	34	31	37
06	41	38	44
07	48	45	51
08	55	52	58
09	62	59	65
10	69	66	72
11	76	73	79
12	83	80	86
13	90	87	93
14	97	94	100
15	104	101	107

Table 3: CTN-0051 Protocol Calendar			
Visit Number	Target Day	Beginning Window (Days)	End of Window (Days)
16	111	108	114
17	118	115	121
18	125	122	128
19	132	129	135
20	139	136	142
21	146	143	149
22	153	150	156
23	160	157	163
24	167	164	195

(2) Participant provides a urine sample positive for non-protocol opioids

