5.3.2 Determination of the Start of the Clinical Qualifying Event

For the purposes of the primary outcome analyses, the relapse start day will be used. The time of the event occurs at the start of the qualifying clinical event period (e.g., first of the 7 consecutive use days or start of the 4 consecutive weeks of use). If both of the criteria above (a and b) are met, then the earlier of the two relapse start dates will define the day that the relapse criterion met for the purposes of primary outcome analyses.

When a participant’s data indicates four consecutive weeks of use, the reason the first week was defined as a use week will be used to determine the start of the qualifying clinical event period. The first use week could be due to either a self-report of at least one day of use, a urine sample positive for non-protocol opioids, failure to provide a urine sample or some combination of these reasons. The following table outlines how the start of the clinical qualifying event will be determined in the case of a participant having four consecutive weeks of use.

Table 4: Determination of the Start of the Clinical Qualifying Event			
Reason for First Use Week			Start of the Clinical Event
Missing UDS	Positive UDS	Self-report of at least one day	
*		*	Date of first self-reported use
	*	*	Day of first self-reported use
		*	Day of first self-reported use
	*		Day of positive urine drug screen
*			First study day of the first use week period as defined by the protocol calendar

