5.3.3 Primary Outcome Analysis Methods

Since the results of the interim analysis indicated a differential treatment initiation rate assessment, the data analysis modification will be employed. As noted in Section 3.2, if there is a differential treatment initiation rate in the early randomizers group, an interaction term for the treatment by randomization timing variables will be incorporated into the final analysis model.

Data will be analyzed using a Cox proportional hazards model. The model is as follows:

$$\log h(t | CUF) = \log h_0(t | CUF) + \beta_1 * Treatment + \beta_2 * TIMING + \beta_3 * CTP + \beta_4 * STRATA + \beta_5 * Treatment * TIMING$$

where h is the hazard rate, roughly defined as the probability per time unit that a case that has not relapsed to the beginning of the respective interval will relapse in that interval. Conceptually, it can be thought of as the number of relapse per time units in the respective interval, divided by the average number of non-relapse cases at the mid-point of the interval. The quantity h0 is an arbitrary baseline hazard rate.

The SAS PHREG procedure will perform survival analysis based on the Cox model to estimate the hazard ratio for the treatments. The 95% Wald Confidence limits will be estimated.

The following SAS Code will be used to analyze the data:

```
PROC PHREG;
    CLASS TREATMENT (REF='BUP-NX') TIMING (REF='Late');
    MODEL TIME*STATUS = TREATMENT TIMING CTP STRATA
    TREATMENT*TIMING;
    HAZARDRATIO TREATMENT;
RUN;
```

The variables included in the SAS code are described as follows:

- TREATMENT- This variable defines the randomized treatment assignment. (BUP-NX or XR-NTX)
- TIME- Time to relapse
- STATUS- Censoring variable
- CTP- CTP
- STRATA- Randomization Stratification factor pertaining to the baseline opioid severity level classified as <6 bags (Low Severity) or ≥ 6 bags (High Severity).
- TIMING- Binary baseline variable (early vs. later randomization as noted in Section 5.1 defined as either 'Late' or 'Early').

The initial analysis will be the construction of the asymptotic 95% CI for the hazard ratio of the difference between the treatment arms in the time to event distribution for the primary outcome. The study arm success rates with confidence intervals at week 24 and the difference in success rate at that time point and associated confidence intervals will be constructed.

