Participant failed naloxone challenge			
Participant failed to provide a negative urine sample			
Participant left prior to induction			
Participant rejected treatment assignment			
Participant met criteria for relapse			
Participant reached end of induction window			
Time to Study Medication Induction (days)			
Mean			
SD			
Median			
Min			
Max			

Table 7: Summary of Induction Status for the Groups of Interest				
	BUP-NX (N=)		XR-NTX (N=)	
	Inducted N (%)	Not Inducted N (%)	Inducted N (%)	Not Inducted N (%)
Total				
Randomization Timing Status				
Early Randomizers				
Late Randomizers				
Opioid Severity Level ¹				
Low Severity				
High Severity				
Randomization Timing Status by Opioid Severity Level				
Early Randomizers and Low Severity				
Early Randomizers and High Severity				
Late Randomizers and Low Severity				
Late Randomizers and High Severity				
Baseline Preference ²				
Preferred Neither Treatment				
BUP-NX Preference				
XR-NTX Preference				
Preferred Either Treatment				

¹ Number of bags is assigned a 0 if the primary opioid of use in the last 7 days was not heroin or the route of administration is not IV-injection. For IV heroin users where the quantity is not provided in bags but in dollars, bags are estimated as the dollar amount/10 rounded to the nearest integer.

² Baseline preference is captured on the Motivation for Participating, Attitudes Regarding Study Medication form. The two questions to address preference are “I would prefer to receive Buprenorphine-Naloxone (Suboxone)” and “I would prefer to receive Naltrexone monthly injections” with responses to each on a 1 -5 scale of agreement with 1 indicating Strongly Disagree and 5 indicating Strongly Agree. If a participant indicates agreement or strong agreement, he/she will be deemed as having preferred that treatment. If the participant indicated agreement for both questions, he/she will be categorized as preferred either.

Table 8: Summary of Early Medication Terminations* by Treatment Arm			
	Treatment Arm		
	BUP-NX (N=)	XR-NTX (N=)	Total (N=)
Number of Early Medication Terminations - N (%)			
Reasons for Early Medication Termination			
Participant became pregnant			
Participant feels study treatment no longer necessary, not working			
Participant became incarcerated			
Participant withdrew consent			
Participant moved from area			
Participant deceased			
Participant met criteria for relapse			
Participant unable to tolerate side effects			

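### The as-treated relapse comparison keeps only inducted participants, yet time to relapse has no origin other than randomization, so inductions after about Day 21 would tilt it towards XR-NTX

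*SAP*

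**What the plan says.** SAP 3.6 (Analysis Populations) defines the set: "The as-treated population will consist of only participants who were inducted onto study medication". It adds that major differences between ITT and as-treated results will be explored further.

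Four other provisions bear on that set.

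- **Induction window.** SAP 1.2, Phase 2: "Induction should occur as soon as practicable following randomization, but may occur as late as week 22". SAP 5.2.1 adds that "the definition of induction status is not dependent upon the number of days for induction to occur".
- **Clock.** SAP 5.3.1: "Relapse assessment starts Day 21 post-randomization with the day of randomization as Day 0 and ends at the Week 24 visit". In the Cox code of SAP 5.3.3 the time variable is described only as "TIME- Time to relapse". There is no entry time, landmark or time-dependent induction term.
- **Relapse closes the door to induction.** Protocol 10.1: "Participants meeting relapse criteria discontinue medication and research visits". In the SAP Appendix A shell for Table 6, "Participant met criteria for relapse" is a listed reason for induction failure.
- **Dating of relapse.** SAP 5.3.2: "The time of the event occurs at the start of the qualifying clinical event period".

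The SAP starts a clock at induction in one place only, the treatment-exposure summary (Appendix A, Table 11). The shells for Tables 16 and 18 carry a row for inducted participants, by arm, for time to relapse and relapse status.

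**The concern.** Membership of the as-treated set is decided after randomization by an event that relapse can prevent. A participant who meets the relapse criteria before being inducted is left out. One who is inducted late stays in, and follow-up before induction is counted as if relapse could have been recorded then. This is guaranteed (immortal) time. No event in either arm can be dated before Day 21, so only inductions after Day 21 add guaranteed time that differs between arms.

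The documents expect the delay on the XR-NTX side. SAP 3.2 explains that XR-NTX must wait for completed detoxification and BUP-NX need not. SAP 5.3.3 records that the interim assessment triggered the modification for differential initiation. That shows different induction rates among early randomizers; it does not report delays.

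At stake is the interpretation of a planned ITT versus as-treated contrast. Part of any apparent gain for XR-NTX among inductees could come from how the set and clock are built.

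**Working it through.** **1. The plan's own figures.** Take 40% success at 6 months, exponential failure, 200 per arm, two-sided 5% (SAP 3.3). Events = 200 × 0.60 + 200 × (1 − 0.40^HR), and power = Φ(½·√events·|ln HR| − 1.96).

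- HR 0.633: survival 0.40^0.633 = 56.0%, 208 events, power 0.910 (SAP: 90%).
- HR 0.678: survival 53.7%, 212.5 events, power 0.809 (SAP: 80%, survival 53.8%).

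The event model reproduces, so it is used below.

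**2. Guaranteed time: inputs.**

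- True HR 1; the SAP's exponential model with events grouped at Day 21; 1,000,000 simulated per arm.
- A participant is dropped if the relapse criteria are met before the assigned induction day.
- Back-dating: the longest qualifying period is 4 weeks, so onset can precede the day criteria are met by up to about 28 − 1 = 27 days.
- *Assumption, not in the documents:* 5-30% of the XR-NTX arm has an induction date after Day 21, uniform over Day 21-63 or over Day 21-156; all BUP-NX participants are inducted by Day 21.

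**3. One case by hand.** Take 30% late, Day 21-156, no back-dating. With k = −ln(0.40)/168 = 0.005454 per day, the mean of e^(−kD) over D = 21 to 156 is (0.892 − 0.427)/(0.005454 × 135) = 0.631. The fraction inducted is 1 − 0.30 × (1 − 0.631) = 0.889. No 24-week success is dropped, so success among XR-NTX inductees is 0.40/0.889 = 45.0%, against 40% on BUP-NX. The ratio of cumulative hazards is 0.799/0.916 = 0.87. The simulated Cox HR is 0.86.

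**4. Simulated as-treated HR (XR-NTX/BUP-NX), clock from randomization.**

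| XR-NTX arm with induction date after Day 21 | Day 21-63, no back-dating | Day 21-63, 27 days | Day 21-156, no back-dating | Day 21-156, 27 days |
|---|---|---|---|---|
| 0% | 1.00 | 1.00 | 1.00 | 1.00 |
| 5% | 0.99 | 1.00 | 0.97 | 0.98 |
| 10% | 0.97 | 0.99 | 0.95 | 0.97 |
| 20% | 0.94 | 0.98 | 0.90 | 0.93 |
| 30% | 0.91 | 0.98 | 0.86 | 0.89 |

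The ITT HR in the same runs is 0.996-1.003. Delayed entry at induction, run without back-dating only, returns 0.997-1.003.

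**5. Selection, a separate effect.** Suppose nobody is inducted late, but XR-NTX participants whose onset precedes an induction date in Day 0-21 are dropped. Then 94.5% are inducted and the HR is 0.92. Delayed entry leaves it at 0.92, because those onsets are all dated to Day 21 and entry falls earlier. Adding 10% late inductions (Day 21-63) gives 0.89, and delayed entry brings it back only to 0.92.

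An extreme bound uses the induction rates at the edge of the decision rule in SAP 3.2: 0.85 for BUP-NX and 0.85 − 0.25 = 0.60 for XR-NTX. If every non-inductee relapses, success among inductees is 0.40/0.60 = 67% versus 0.40/0.85 = 47%. The HR is ln(0.667)/ln(0.471) = 0.405/0.754 = 0.54 with no true effect. This is a limit, not a forecast.

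**The case against.** The strongest case on the other side has four parts.

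- **No origin is named for this set.** SAP 3.6 gives none, and the rows for inductees in Tables 16 and 18 are descriptive. That is true. But SAP 3.6 says the primary and secondary efficacy outcomes are to be analysed by population and that ITT and as-treated results will be compared, and randomization is the only origin the SAP defines for time to relapse.
- **Delays may be short.** About 350 of 600 participants are expected to be late randomizers, whom SAP 1.3.1 describes as readily inducted onto either drug. If only the early randomizers (250/600 = 42%) are delayed, by a mean of 7-20 days, the HR is 0.96-1.00 without back-dating and 0.99-1.00 with the maximum. This stands, and the bias may be negligible.
- **The primary model includes timing and its interaction with treatment.** That separates early from late randomizers. It does not remove guaranteed time; it would concentrate it in whichever group has the delays.
- **Table 6 will show time to induction and reasons for failure by arm.** This helps a careful reader, but does not correct the estimate.

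Two stronger readings are tempting. A reader might infer that every late inductee was relapse-free until induction. Back-dating rules this out: onset may precede induction, provided the criteria had not yet been met. A reader might also expect HRs near 0.84 or 0.79. Those need all XR-NTX inductees to be delayed by a mean of 40 or 60 days, which does not fit the expected share of late randomizers.

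**Conclusion.** The concern holds for the as-treated comparison only. The mechanism follows from the documents; its size does not. Over the assumed range the HR under no effect is 0.86-0.99 without back-dating and 0.89-1.00 with maximum back-dating. It is 1.00 if nobody is inducted after Day 21. The direction rests on the expectation that XR-NTX induction is slower, since the week-22 window applies to both arms.

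Dropping induction failures pushes the same way and can matter more. It would remain even with a correct clock, so delayed entry alone does not make the comparison a valid estimate of the effect of receiving the drug.

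It would be wrong to infer that the trial's main result is biased: SAP 5.4 places all randomized participants in the primary efficacy analysis. Nor does the SAP say that a difference between the two sets will be read as a drug effect. It simply does not warn against that reading.

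**What to change.** In SAP 3.6 and 5.3.3:

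1. Fit the inducted-set Cox model with delayed entry at the induction day (the `ENTRY=` option in PHREG), using the primary model's covariates.
2. State that inductees whose back-dated onset precedes induction contribute no risk time, and report their number by arm.
3. Call the set the inducted population, and label its result a non-randomized, supportive comparison.
4. Show it beside the time-to-induction summary already planned in Table 6, and keep treatment conclusions on ITT.

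The cost is one model option, one count by arm and a few sentences. A few events are lost from a supportive analysis. The selection bias remains, which is why the label is needed as well as the code change.
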